10.2 Dose Reduction

10.2.1 Definition of Dose-Modification Toxicity

Dose-modification toxicity will be defined as any of the following events that are possibly, probably or definitely attributable to trametinib.

Dose modifying hematological and non-hematological toxicities are defined differently.

10.2.1.1 Non-Hematological Dose-Modifying Toxicity

- See [Section 10.2.6](#) for management guidelines for toxicities of special interest. Note that dose modification or discontinuation of trametinib for toxicity is considered a dose modifying toxicity.
- Any Grade 4 non-hematological toxicity with specific exclusion of:
 - Grade 4 fever/pyrexia that resolves to Grade < 2 within 72 hours with supportive care (anti-pyretics)
- Dose-modifying hypertension will be considered as the following:
 - Grade 4 hypertension,
 - A blood pressure > 25 mm Hg above the 95th percentile for age, height, and gender, confirmed by repeated measurement

Note: if elevated, take 3 serial blood pressure readings from the same extremity with the patient in the same position, separated by at least 5 minutes. Avoid using the lower extremity if possible. Use the mean average of the 3 measurements.

- Any Grade 3 non-hematological toxicity with the specific exception of:
 - Grade 3 nausea and vomiting of less < 3 days duration

- Grade 3 fever or infection < 7 days duration.
- Grade 3 hypophosphatemia, hypokalemia, hypocalcemia and/or hypomagnesemia responsive to oral supplementation within 7 days
- Grade 2 allergic reactions that necessitate discontinuation of study drug will not be considered a dose-modifying toxicity
- Any Grade 2 non-hematological toxicity that persists for ≥ 7 days and is considered sufficiently medically significant or sufficiently intolerable by patients that it requires treatment interruption
- Grade 2 left ventricular ejection fraction disease
- Grade 2 cardiac valvular toxicity (mitral/aortic/tricuspid)
- Grade 2 pneumonitis
- Treatment interruption longer than 14 days due to delayed recovery from toxicity will be cause for dose modification

10.2.2 Hematological Dose-Modifying Toxicity

Hematologic will be defined as failure to recover a peripheral ANC $> 500/\mu\text{L}$ and platelets $> 20,000/\mu\text{L}$ by 42 days after the first treatment day, not due to malignant infiltration.

Note: Grade 4 febrile neutropenia will not be considered a dose-modification toxicity.

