10.2.4 Dose Modifications for Hematologic Toxicity

The study chair must be notified for any dosage modification or use of myeloid growth factors.

- If a subject experiences a dose modifying hematologic toxicity as defined in [Section 10.2.2](#), the treatment will be held until improvement to Grade 3 or less.
- Subjects will be allowed 1 episode of Grade 4 hematologic toxicity without dose reduction.
- If there is > 1 hold for Grade 4 hematologic toxicity, dose will be reduced per guidance in [Appendix II](#). Counts should be checked twice weekly during this time.
- Doses reduced for toxicity will not be re-escalated, even if there is minimal or no toxicity with the reduced dose.
- If dose-modifying toxicity recurs in a subject who has resumed treatment at the reduced dose, the subject must be removed from protocol therapy.

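### The hematologic dose-hold rule rests on a day-42 landmark that does not fit continuous dosing, and Sections 10.2.4 and 10.10 give conflicting actions with no stated precedence

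*Protocol*

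**What the plan says.** **The definition.** Protocol 10.2.1 sets an attribution test for all dose-modifying events: "Dose-modification toxicity will be defined as any of the following events that are possibly, probably or definitely attributable to trametinib". For blood counts, 10.2.2 then gives one criterion, failure to regain ANC above 500/µL and platelets above 20,000/µL "by 42 days after the first treatment day, not due to malignant infiltration". It adds one exclusion: "Note: Grade 4 febrile neutropenia will not be considered a dose-modification toxicity".

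**The specific action rule.** Section 10.2.4 opens with a central check: "The study chair must be notified for any dosage modification or use of myeloid growth factors". For a toxicity meeting the 10.2.2 definition, "the treatment will be held until improvement to Grade 3 or less". A first Grade 4 event costs no dose: "Subjects will be allowed 1 episode of Grade 4 hematologic toxicity without dose reduction". From the second such hold onward the dose drops as Appendix II sets out, and it may not go back up afterwards. The section ends with a removal rule: "If dose-modifying toxicity recurs in a subject who has resumed treatment at the reduced dose, the subject must be removed from protocol therapy".

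**The general action rule.** Section 10.10 opens by noting that hematologic and non-hematologic dose-modifying toxicities have different definitions. It then prints a grade-based table for adverse events. At Grade 3, or Grade 2 that is not tolerated, drug is stopped until Grade 0-1 and resumed one level lower. At Grade 4, drug is either stopped for good or handled in that same way. Hematologic events are not exempted.

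**Context.** Dosing is continuous for up to 24 cycles of 28 days (4.3.1), or 36 with the extension (4.5). Section 2.1 allows each subject one dose reduction, and Appendix II lists one reduced level. Section 4.3.1 refers sites to Section 10 as a whole for dose modification.

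**The concern.** There are two separate defects.

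First, the 10.2.2 criterion asks whether counts have come back by a fixed day after the start of treatment. That is the logic of a count nadir followed by recovery, with marrow disease as the competing explanation. In this trial drug is given every day for about two to three years, and 5.2 excludes most subjects with recent or current malignancy. A count that falls for the first time in, say, cycle 8 has no natural place in the definition, yet the explicit hold in 10.2.4 depends on it.

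Second, a site facing a Grade 4 cytopenia finds two sets of instructions in Section 10 that cannot both be followed, and nothing says which one controls. At stake is consistent patient management. With one reduction available and no way back up under 10.2.4, the choice of rule decides whether a subject keeps full dose, uses the only reduction or leaves therapy.

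**Working it through.** The plan gives no figure to reproduce here. The check compares the texts, with a little arithmetic for size.

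**Step 1: where the landmark falls.** Inputs: day 42 (10.2.2); 28-day cycles, 24 planned (4.3.1); 36 with extension (4.5).

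- Day 42 = 42/28 = 1.5 cycles.
- Treatment phase: 24 × 28 = 672 days; 672 − 42 = 630 days remain, and 630/672 = 93.8%.
- With extension: 36 × 28 = 1,008 days; 1,008 − 42 = 966 days remain, and 966/1,008 = 95.8%.

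**Step 2: what triggers a hold in 10.2.4.** The first bullet is the only one that tells the site to hold drug, and it is limited to toxicity as 10.2.2 defines it. The second and third bullets use a different term, Grade 4 hematologic toxicity, without referring to 10.2.2. They speak of episodes and of more than one hold, so they presuppose Grade 4 holds beyond the landmark, but neither orders one. The intention can be inferred; the instruction is not printed.

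**Step 3: 10.2.4 and 10.10 side by side.**

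| Situation | 10.2.4 | 10.10 table |
|---|---|---|
| Restart after a hold | Grade 3 or less | Grade 0-1 |
| First Grade 4 episode | No dose reduction | One-level reduction, or permanent discontinuation |
| Grade 3 cytopenia | No hold ordered; a grade at which dosing may resume | Hold and reduce one level |

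The highest permitted restart grades differ by 3 − 1 = 2.

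**Step 4: what the first-episode difference costs in dose.** For a subject on Dose Level 1, 10.2.4 costs nothing. If therapy continues under 10.10, the cost is one level (Appendix II):

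- Nominal: (0.025 − 0.020)/0.025 = 20%.
- 35-50 kg: (1 − 0.75)/1 = 25%.
- 50.1-70 kg: (1.5 − 1)/1.5 = 33.3%.
- 70.1 kg and above: (2 − 1.5)/2 = 25%.

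That is the single reduction 2.1 allows.

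**Step 5: what does not move.** The efficacy endpoint is a composite of imaging, patient-reported outcome and clinical benefit (8.3.2), and its definition does not use the hold rules. Adverse event recording follows 10.6. The severe toxicities listed for the 9.2 stopping rule include no hematologic event, so its boundaries stay as they are. The Simon design figures in 9.1 do not depend on any of this.

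**The case against.** The strongest reply is that the text works if read with ordinary sense. The later bullets of 10.2.4 show that Grade 4 holds at any time were intended. Section 10.1.2 permits interruption for any safety reason, 10.10 would interrupt at Grade 4, and investigators may withdraw a subject in any case. Section 10.10 is a generic table, and a specific rule normally overrides a general one. The protocol departs from the table elsewhere too: 10.2.6.7 lets a subject resume without reduction after Grade 3 diarrhea that settles within 72 hours, where the table would reduce. The study chair hears of every dosage modification, and 10.2.6 lists no cytopenia as an event of special interest.

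Much of this stands, and it rules out stronger conclusions that a reader might infer:

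- *That late cytopenias go unheld.* The documents do not support this, because 10.1.2 and 10.10 both allow the interruption.
- *That the repeat-episode bullets of 10.2.4 cannot operate, since one landmark gives at most one hold.* That requires reading the 10.2.2 definition into bullets that use their own term.
- *That subjects would leave therapy a set number of episodes earlier under 10.10.* The table prints no rule for a second event once no lower level remains.
- *That a given share of subjects will be affected.* The protocol gives no Grade 4 cytopenia rate, so any such probability would rest on an unanchored assumption.
- *That the cycle-start counts in Appendix IX add to the conflict.* No body section cites that worksheet, and part of the comparison with 5.1 turns on uncertain units. It is a separate, minor tidy-up.

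The reply does not remove the printed contradiction. Nothing in the protocol says that 10.2.4 overrides 10.10. Notifying the study chair supplies no rule to apply, and permission to interrupt settles neither the restart grade nor the dose. Taking the first treatment day to mean day 1 of each cycle does not help either: the test would then fall 42 − 28 = 14 days into the following cycle.

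**Conclusion.** The point holds in two limited parts. The day-42 and malignant-infiltration definition is wrong for this trial, and, read literally, 10.2.4 orders no hold for a Grade 4 cytopenia that begins after day 42. Sections 10.2.4 and 10.10 also contradict each other on restart grade (3 or less versus 0-1) and on the first Grade 4 episode (no reduction versus reduction or permanent discontinuation), with no precedence stated.

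The dose at stake is one level, nominally 20%, and 25% to 33.3% on the nomogram at 35 kg or more, taken from the only reduction available. These percentages assume a subject on Dose Level 1. The first-episode contrast assumes that the Grade 4 bullets of 10.2.4 apply whenever the event occurs, which is their natural meaning. How often the conflict would arise cannot be said from the protocol.

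This is a patient-management defect to correct by amendment. It does not threaten the trial's primary inference or its safety stopping rule.

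**What to change.** - **10.2.2:** Replace the day-42 and malignant-infiltration wording with Grade 4 hematologic toxicity at least possibly attributable to trametinib, at any time on treatment. This keeps the 10.2.1 attribution test. Retain the febrile-neutropenia note. The sponsor should set the exact count thresholds and say how baseline cytopenia in Kaposiform lymphangiomatosis is handled.
- **10.10:** State that hematologic toxicity follows 10.2.4.

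The cost is one text amendment, with no new visits, procedures or subjects. The downside is that somewhat more events would be classed as dose-modifying.

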10.2.3 Dose Modifications for Non-Hematologic Toxicity

If a subject experiences a dose-modifying non-hematologic toxicity as defined in [Section 10.2.1](#), the treatment will be held.

If the toxicity does not resolve to meet inclusion/exclusion parameters or baseline within 14 days of drug discontinuation the subject must be removed from protocol therapy unless specifically documented in toxicities of special interest [Section 10.2.6](#).

If the toxicity resolves to meet inclusion/exclusion parameters or baseline within 14 days of drug discontinuation the subject may resume treatment with a reduction to the next lower dose according to [Appendix II](#). See [Appendix II](#) for dosing modification in subjects receiving oral solution or the specified dose reduction in subjects receiving tablets.

- Doses reduced for toxicity will not be re-escalated, even if there is minimal or no toxicity with the reduced dose, unless otherwise specified in the toxicities of special interest [Section 10.2.6](#).
- If the same dose-modifying toxicity recurs in a subject who has resumed treatment, the subject must be removed from protocol therapy.

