10.2.5 Dose Modifications for Hepatic Toxicity

If a subject experiences Grade ≥ 3 ALT or AST or total bilirubin elevation, treatment will be held. If toxicity resolves to meet eligibility criteria within 7 days, the drug may be resumed at the same dose. Grade ≥ 3 ALT or AST or bilirubin that persists ≥ 7 days will be considered dose-modifying and require dose modification per [Section 10.1.3](#).

Grade	0	1	2	3	4
SGOT (Serum glutamic oxaloacetic transaminase) (AST)	WNL	>ULN to 3x ULN	>3 to 5x ULN	>5 to 20x ULN	>20x ULN
SGPT (Serum glutamic pyruvic transaminase) (ALT)	WNL	>ULN to 3x ULN	>3 to 5x ULN	>5 to 20x ULN	>20x ULN
Bilirubin	WNL	>ULN to 1.5x ULN	>1.5 to 3x ULN	>3 to 10x ULN	>10x ULN

Safety Follow-Up Procedures for subjects with ALT or AST ≥ 3 times ULN or bilirubin ≥ 1.5 times ULN:

- Monitor subjects weekly until liver chemistries resolve, stabilize, or return to within baseline values.

Safety Follow-Up Procedures for subjects meeting DLT criterion as above (ALT or AST ≥ 5 times ULN and bilirubin ≥ 3 times ULN) greater than 7 days:

- This event is considered an DLT.
- Serum bilirubin fractionation should be performed if testing is available. If fractionation is unavailable, urinary bilirubin is to be measured via dipstick (a measurement of direct bilirubin, which would suggest liver injury).
- Subjects should have close follow-up for repeat liver chemistries, additional testing, and close monitoring (with specialist or hepatology consultation recommended).
- Monitor subjects twice weekly until liver chemistries (ALT, AST, ALP, and bilirubin) resolve, stabilize or return to within baseline values.

- In addition, every attempt should be made to carry out the liver event follow-up assessments described below:
 - Viral hepatitis serology, including:
 - Hepatitis A IgM antibody
 - Hepatitis B surface antigen and Hepatitis B Core Antibody (IgM)
 - Hepatitis C RNA
 - Cytomegalovirus IgM antibody
 - Epstein-Barr viral capsid antigen IgM antibody (or if unavailable, then obtain heterophile antibody or monospot testing)
 - Serum creatine kinase (CK) and lactate dehydrogenase (LDH).
 - Fractionate bilirubin, if total bilirubin ≥ 2 X upper limit of normal (ULN).
 - Obtain a complete blood count (CBC) with differential to assess eosinophilia.

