Symptomatic ^{c,d}	
Ejection fraction decreased:
 
 • Grade 3: resting LVEF 39-20% or \geq 20% absolute reduction from baseline • Grade 4: Resting LVEF \leq 20%. 
Left Ventricular Systolic Dysfunction:
 
 • Grade 3: Symptomatic due to drop in ejection fraction responsive to intervention. 	
 • Permanently discontinue trametinib. • Report as SAE. • Consult with cardiologist. • Repeat ECHO/MUGA after 2, 4, 8, 12, and 16 weeks or until resolution.

	
 Grade 4: Refractory or poorly controlled heart failure due to drop in ejection fraction; intervention such as ventricular assist device, intravenous vasopressor support, or heart transplant indicated. 	

^a If ECHO/MUGA does not show LVEF recovery after 2 weeks, repeat ECHO/MUGA 2 weeks later.
 
^b Escalation of trametinib to previous dose level can be considered if LVEF remains stable for 4 weeks after restarting of trametinib. Approval from the study chair is required.
 
^c Symptoms associated with a decreased ejection fraction may include dyspnea, orthopnea, and other signs and symptoms of pulmonary congestion and edema.
 
^d Symptoms associated with a decreased ejection fraction can be graded as per CTCAE v5.0 criteria for Left Ventricular Systolic Dysfunction and/or Ejection fraction decreased.
		

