 - If diarrhea resolves to Grade \leq 1 or baseline within 72 hours of anti-diarrheal measures or supportive care measures, may resume study treatment without dose reduction as per [Section 10.2.3](#). If diarrhea Grade \geq 3 recurs subject is not eligible for resumption of treatment without dose reduction.
 - If diarrhea resolves to Grade \leq 1 or baseline >72 hours but within 7 days, then may resume study treatment with a dose reduction as per [Section 10.2.3](#).
 - If diarrhea does not resolve to Grade \leq 1 or baseline in \leq 7 days without study treatment, discontinue protocol therapy.

For Grade 4 diarrhea:

- If loperamide has not been initiated, initiate loperamide immediately using institutional or protocol guidelines for dosing as above. For dehydration, use intravenous fluids as appropriate; if severe dehydration, consider administration of octreotide.
- Hold study treatment until symptoms resolve to \leq Grade 1 or baseline.
 - If diarrhea resolves to Grade \leq 1 or baseline \leq 7 days without study treatment, then may resume study treatment with a dose reduction as per [Section 10.2.3](#).
 - If diarrhea does not resolve to Grade \leq 1 or baseline in \leq 7 days without study treatment, discontinue protocol therapy.

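### Section 10.2.3 orders removal on any recurrence of a dose-modifying non-hematologic toxicity, which conflicts with the restart rules for diarrhea (by implication) and rash in Section 10.2.6

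*Protocol*

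**What the plan says.** **General rule.** Section 10.2.1.1 counts as dose-modifying "Any Grade 3 non-hematological toxicity with the specific exception of" a short list, and diarrhea is not on that list. Section 10.2.3 holds treatment for such an event and allows resumption at the next lower dose. On recurrence it says: "If the same dose-modifying toxicity recurs in a subject who has resumed treatment, the subject must be removed from protocol therapy".

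**Diarrhea.** Under Section 10.2.6.7, a subject whose Grade 3 diarrhea settles within 72 hours "may resume study treatment without dose reduction as per" Section 10.2.3. If Grade 3 or higher diarrhea "recurs subject is not eligible for resumption of treatment without dose reduction". The next bullet covers diarrhea that takes more than 72 hours to settle "but within 7 days, then may resume study treatment with a dose reduction as per" Section 10.2.3.

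**Rash.** In Section 10.2.6.3, the row labelled Other deals with intolerable rash that keeps coming back and has already led to two interruptions of a week or more. It interrupts treatment until recovery, restarts at the next lower dose, and discontinues only if the rash is still intolerable.

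**Dose levels.** Section 2.1 allows one dose reduction, and Appendix II lists nothing below level -1.

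**The concern.** A general rule and its toxicity-specific rules should give the same instruction for the same subject. Here the general rule says remove, while the specific rules leave a restart open (diarrhea) or direct one (rash). A site that restarts the subject breaches a mandatory sentence in Section 10.2.3. A site that removes the subject may end treatment for someone whom Section 10.2.6 would have kept on a lower dose. Rash and diarrhea are both listed as events of special interest in Section 10.2.6, and about 25 sites will apply these rules. What is at stake is consistent safety management and consistent discontinuation, not the statistical design.

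**Working it through.** No rate or formula applies to the conflict itself, so the check sets the rules side by side. It assumes that the event is attributed to trametinib, as Section 10.2.1 requires.

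1. **Is the diarrhea dose-modifying?** Yes. The Grade 3 exceptions in Section 10.2.1.1 concern short nausea and vomiting, short fever or infection, and electrolyte disturbances that respond to supplements. At Grade 4 only short-lived fever is excluded.

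2. **One subject followed through.** Grade 3 diarrhea settles within 72 hours, the subject restarts at full dose, Grade 3 diarrhea returns, and it settles within 7 days.
   - Section 10.2.3: the same dose-modifying toxicity has recurred after resumption, so the subject is removed.
   - Section 10.2.6.7: a full-dose restart is barred. That sentence would have no purpose if every recurrence meant removal, and the neighboring bullet offers a reduced-dose restart. The implied action is to resume at level -1.

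3. **The rash row.** Section 10.2.1.1 also counts Grade 2 toxicity that lasts at least 7 days and is intolerable enough to need interruption. Two week-long interruptions for intolerable rash can therefore be two dose-modifying events. Section 10.2.3 would remove the subject at the second. The row instead directs a restart at a lower dose.

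4. **Does Section 10.2.3 defer to Section 10.2.6?** Two of its rules do. The 14-day rule says the subject "must be removed from protocol therapy unless specifically documented in toxicities of special interest", and the ban on re-escalation carries a similar exception. The recurrence bullet carries none.

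5. **How neighboring sections handle it.** Section 10.2.4 (hematologic) orders removal only when toxicity recurs at the reduced dose. Section 10.2.5 (hepatic) says "If toxicity resolves to meet eligibility criteria within 7 days, the drug may be resumed at the same dose" and treats only elevations lasting 7 days or more as dose-modifying. Section 10.2.6.7 has neither device.

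6. **Cross-reference.** Section 10.2.6.7 cites Section 10.2.3 for the full-dose restart, but Section 10.2.3 offers only the next lower dose.

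7. **Appendix II, oral solution.** A reduced-dose restart is only a reduction if level -1 is below level 1.
   - 9.0-9.9 kg: 0.12 mg at level 1 and 0.18 mg at level -1. 0.18 / 0.12 = 1.5, so the step down raises the dose by 50%. The level 1 entry is marked as 0.0125 mg/kg, while 0.18 mg equals 0.020 mg/kg x 9.0 kg.
   - 10.0-10.9 kg: 0.2 mg at both levels, so the step down changes nothing.
   - 11 kg and above: every row is lower at level -1 (for example 0.25 mg to 0.22 mg at 11-11.9 kg).

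**The case against.** The strongest defence is that the texts can be reconciled. The only resumption that Section 10.2.3 describes is at the lower dose, so its recurrence bullet could be read as meaning recurrence at that dose. The first bullet of Section 10.2.1.1 also sends the reader to Section 10.2.6 for toxicities of special interest, and the schedule in Section 10.10 calls for a one-level reduction on resuming after Grade 3. A site would probably turn to the diarrhea section first.

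Part of this stands. Section 10.2.6.7 never says outright that a reduced-dose restart is allowed after recurrence, and a site that removes the subject breaks nothing in that section. A reader might infer an express contradiction there; the text supports only an implied one.

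The rest is weaker. Section 10.2.4 writes out the reduced-dose limit and Section 10.2.3 does not. Section 10.2.3 also says where Section 10.2.6 prevails and leaves the recurrence bullet out, so a site may take the omission as intended.

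A reader might also suppose that only the diarrhea sequence is affected. The rash row shows otherwise, and an exception written for diarrhea alone would leave the rash conflict in place.

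**Conclusion.** The concern holds as a minor drafting conflict: by clear implication for diarrhea, and by a direct restart instruction for rash wherever the interruptions count as dose-modifying. How often it will arise cannot be computed, because the protocol gives no rate of recurrent Grade 3 or higher diarrhea or of repeated rash interruption in this population. The number is probably small.

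A reader might infer that removal turns a subject into a non-responder and so biases the primary endpoint. The protocol does not support that. Section 8.1 schedules end-of-treatment assessments for subjects who stop early, Section 8.3.1 makes a subject evaluable after one cycle and a re-evaluation, and Section 8.3.2 counts stable disease as a clinically meaningful response. The two-stage design and the toxicity boundary in Section 9.2 are unaffected.

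The two Appendix II rows are a separate defect. They affect every dose reduction at those weights, whatever the toxicity, and they do not bear on whether the recurrence rules conflict.

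**What to change.** 1. **Section 10.2.3, recurrence bullet.** Require removal when the same dose-modifying toxicity recurs in a subject whose dose has already been reduced for that toxicity, including after any re-escalation. This follows the limit in Section 10.2.4. The re-escalation clause matters because Section 10.2.6.5 says "Escalation of trametinib to previous dose level can be considered if LVEF remains stable for 4 weeks after restarting of trametinib", and Section 10.2.6.6 has a similar footnote for pneumonitis; without the clause the rule would be loosened for those events. The Grade 2 rash row lowers the dose without a hold and raises it again on recovery, so keep the present condition that treatment was resumed, to avoid catching that step by accident.
2. **Section 10.2.6.7.** Delete the reference to Section 10.2.3 from the full-dose restart bullet.
3. **Section 10.2.6.3, row Other.** Limit the reduced-dose restart to subjects not already at level -1, and discontinue those who are, because no lower level exists. State as well which rule governs a subject who was reduced, re-escalated for rash and then interrupted again.
4. **Appendix II (separate defect).** Correct the 9.0-9.9 kg and 10.0-10.9 kg oral solution rows so that level -1 is below level 1. The replacement doses are for the sponsor to set.

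The cost is one reworded bullet, one deleted phrase, one qualified table row and two corrected dose rows. No extra subjects, visits or data are needed.
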